Appendix D. Reporting Selected Laboratory Parameters in Conventional Unit

All clinical laboratory parameters will be reported in the International System (SI) units as standard practice. In addition, descriptive statistics for values and changes from baseline in conventional units at all assessed visits will be reported for selected laboratory parameters as listed in Table D-1 below.

Table D-1. List of Selected Parameters to be Reported in Conventional Units

Number	Laboratory Parameter	Conventional Unit	Decimal Places
1	Alanine Aminotransferase (SGPT)	U/L	0
2	Albumin	g/dL	1
3	Alkaline Phosphatase	U/L	0
4	Aspartate Aminotransferase (SGOT)	U/L	0
5	Bilirubin, Direct (Conjugated)	mg/dL	1
6	Bilirubin, Indirect (Unconjugated)	mg/dL	1
7	Bilirubin, Total	mg/dL	1
8	Blood Urea Nitrogen	mg/dL	0
9	Calcium	mg/dL	1
10	Cholesterol, HDL	mg/dL	0
11	Cholesterol, LDL	mg/dL	0
12	Cholesterol, LDL direct and calculated (combined) (This lab parameter could be the same as #11)	mg/dL	0
13	Cholesterol, Total	mg/dL	0
14	Creatine Kinase	U/L	0
15	Creatinine	mg/dL	1
16	Glucose	mg/dL	0
17	Insulin	uIU/mL	1
18	Triglycerides	mg/dL	0
19	Uric Acid	mg/dL	1
20	Hemoglobin	g/dL	1

Patient narratives will also include the values in conventional units for the selected lab parameters (Table D-1). That will be accomplished by presenting the values in conventional units within the parentheses next to the values in SI units. As shown in Table D-2 below for 'Bilirubin, Total' parameter, for which 'umol/L' is the SI unit and 'mg/dL' is the conventional unit.

Table D-2. Presenting Laboratory Data Using SI and Conventional Units in Narratives

LABORATORY DATA						
Lab Test	Test Name	Normal Range		VISIT01	VISIT05	VISIT07
		Low	High	2012-07-03	2012-08-07	2012-09-04
CHEMISTRY	Bilirubin, Total (μmol/L(mg/dL))	0 (0)	18.81 (1.1)	6.84 (0.4)	5.13 (0.3)	5.13 (0.3)

Appendix E. Identifying Prior Exposure (yes/no) to a Migraine Prevention Medications with Proven Efficacy Based on Prior Medications Reported in eCRF

According to Appendix F in the protocol, a list of migraine-preventive medications with proven efficacy was identified by the clinical team and coding team as shown in Table E.

If a subject has taken medications before the screening visit with preferred names in Table E, and the prior medications are classified as "Migraine Prevention Medication" in the prior and concomitant medications eCRF, then the prior exposure to migraine prevention medications with proven efficacy will be "Yes" for this subject, otherwise, it is set as "No."

Table E. A List of Migraine-Preventive Medications with Proven Efficacy

Protocol Pharmacologic Category	Drug Class	Preferred Name
Antiepileptic	valproic acid	CLONAZEPAM;VALPROIC ACID
Antiepileptic	valproic acid	VALPROIC ACID
Antiepileptic	sodium valproate	VALPROATE MAGNESIUM
Antiepileptic	sodium valproate	CLONAZEPAM;VALPROATE SEMISODIUM
Antiepileptic	sodium valproate	VALPROATE SEMISODIUM
Antiepileptic	sodium valproate	VALPROATE SODIUM
Antiepileptic	sodium valproate	VALPROATE SODIUM;VALPROIC ACID
Antiepileptic	Topiramate	PHENTERMINE HYDROCHLORIDE;TOPIRAMATE
Antiepileptic	Topiramate	PHENTERMINE;TOPIRAMATE
Antiepileptic	Topiramate	TOPIRAMATE
Tricyclin antidepressant	Amitriptyline	AMITRIPTYLINE
Tricyclin antidepressant	Amitriptyline	AMITRIPTYLINE HYDROCHLORIDE
Tricyclin antidepressant	Amitriptyline	AMITRIPTYLINE HYDROCHLORIDE;CHLORDIAZEPOXIDE

Protocol Pharmacologic Category	Drug Class	Preferred Name
Tricyclin antidepressant	Amitriptyline	AMITRIPTYLINE HYDROCHLORIDE;CHLORDIAZEPOXIDE HYDROCHLORIDE
Tricyclin antidepressant	Amitriptyline	AMITRIPTYLINE HYDROCHLORIDE;CODEINE PHOSPHATE;DEXTROPROPOXYPHENE HYDROCHLORIDE;METAMIZOLE SODIUM
Tricyclin antidepressant	Amitriptyline	AMITRIPTYLINE HYDROCHLORIDE;DIAZEPAM
Tricyclin antidepressant	Amitriptyline	AMITRIPTYLINE HYDROCHLORIDE;DIAZEPAM;PERPHENAZINE
Tricyclin antidepressant	Amitriptyline	AMITRIPTYLINE HYDROCHLORIDE;GABAPENTIN
Tricyclin antidepressant	Amitriptyline	AMITRIPTYLINE HYDROCHLORIDE;LIDOCAINE HYDROCHLORIDE;PREDNISONE
Tricyclin antidepressant	Amitriptyline	AMITRIPTYLINE HYDROCHLORIDE;MECOBALAMIN
Tricyclin antidepressant	Amitriptyline	AMITRIPTYLINE HYDROCHLORIDE;MEDAZEPAM
Tricyclin antidepressant	Amitriptyline	AMITRIPTYLINE HYDROCHLORIDE;PERPHENAZINE
Tricyclin antidepressant	Amitriptyline	AMITRIPTYLINE HYDROCHLORIDE;PREGABALIN
Tricyclin antidepressant	Amitriptyline	AMITRIPTYLINE HYDROCHLORIDE;PRIDINOL HYDROCHLORIDE
Tricyclin antidepressant	Amitriptyline	AMITRIPTYLINE HYDROCHLORIDE;PROPRANOLOL HYDROCHLORIDE
Tricyclin antidepressant	Amitriptyline	AMITRIPTYLINE HYDROCHLORIDE;TRIFLUOPERAZINE HYDROCHLORIDE
Tricyclin antidepressant	Amitriptyline	AMITRIPTYLINE;CHLORDIAZEPOXIDE
Tricyclin antidepressant	Amitriptyline	AMITRIPTYLINE;CODEINE;DEXTROPROPOXYPHENE; METAMIZOLE
Tricyclin antidepressant	Amitriptyline	AMITRIPTYLINE;DIAZEPAM

Protocol Pharmacologic Category	Drug Class	Preferred Name
Tricyclin antidepressant	Amitriptyline	AMITRIPTYLINE; DIAZEPAM; PERPHENAZINE
Tricyclin antidepressant	Amitriptyline	AMITRIPTYLINE; GABAPENTIN
Tricyclin antidepressant	Amitriptyline	AMITRIPTYLINE; KETAMINE
Tricyclin antidepressant	Amitriptyline	AMITRIPTYLINE; LIDOCAINE; PREDNISONE
Tricyclin antidepressant	Amitriptyline	AMITRIPTYLINE; MECOBALAMIN
Tricyclin antidepressant	Amitriptyline	AMITRIPTYLINE; MEDAZEPAM
Tricyclin antidepressant	Amitriptyline	AMITRIPTYLINE; PERPHENAZINE
Tricyclin antidepressant	Amitriptyline	AMITRIPTYLINE; PREGABALIN
Tricyclin antidepressant	Amitriptyline	AMITRIPTYLINE; PRIDINOL
Tricyclin antidepressant	Amitriptyline	AMITRIPTYLINE; PROPRANOLOL
Tricyclin antidepressant	Amitriptyline	AMITRIPTYLINE; TRIFLUOPERAZINE
Tricyclin antidepressant	Nortriptyline	NORTRIPTYLINE
Tricyclin antidepressant	Nortriptyline	NORTRIPTYLINE; PREGABALIN
Tricyclin antidepressant	Nortriptyline	NORTRIPTYLINE; PERPHENAZINE
Tricyclin antidepressant	Nortriptyline	NORTRIPTYLINE HYDROCHLORIDE
Tricyclin antidepressant	Nortriptyline	NORTRIPTYLINE HYDROCHLORIDE; PREGABALIN
Tricyclin antidepressant	Nortriptyline	NORTRIPTYLINE HYDROCHLORIDE; PERPHENAZINE
Beta-blockers	Metoprolol	ACETYLSALICYLIC ACID; ATORVASTATIN CALCIUM; METOPROLOL SUCCINATE; RAMIPRIL

Protocol Pharmacologic Category	Drug Class	Preferred Name
Beta-blockers	Metoprolol	ACETYLSALICYLIC ACID;ATORVASTATIN;METOPROLOL;RAMIPRIL
Beta-blockers	Metoprolol	ACETYLSALICYLIC ACID;METOPROLOL
Beta-blockers	Metoprolol	ACETYLSALICYLIC ACID;METOPROLOL SUCCINATE
Beta-blockers	Metoprolol	AMLODIPINE BESILATE;METOPROLOL SUCCINATE
Beta-blockers	Metoprolol	AMLODIPINE BESILATE;METOPROLOL TARTRATE
Beta-blockers	Metoprolol	AMLODIPINE;METOPROLOL
Beta-blockers	Metoprolol	AMLODIPINE;METOPROLOL SUCCINATE
Beta-blockers	Metoprolol	AMLODIPINE;METOPROLOL TARTRATE
Beta-blockers	Metoprolol	ATORVASTATIN CALCIUM;METOPROLOL SUCCINATE
Beta-blockers	Metoprolol	ATORVASTATIN CALCIUM;METOPROLOL TARTRATE;RAMIPRIL
Beta-blockers	Metoprolol	ATORVASTATIN;METOPROLOL
Beta-blockers	Metoprolol	ATORVASTATIN;METOPROLOL;RAMIPRIL
Beta-blockers	Metoprolol	BENIDIPINE HYDROCHLORIDE;METOPROLOL SUCCINATE
Beta-blockers	Metoprolol	BENIDIPINE;METOPROLOL
Beta-blockers	Metoprolol	CHLORTALIDONE;CILNIDIPINE;METOPROLOL
Beta-blockers	Metoprolol	CHLORTALIDONE;METOPROLOL
Beta-blockers	Metoprolol	CHLORTALIDONE;METOPROLOL SUCCINATE
Beta-blockers	Metoprolol	CHLORTALIDONE;METOPROLOL SUCCINATE;TELMISARTAN
Beta-blockers	Metoprolol	CHLORTALIDONE;METOPROLOL TARTRATE
Beta-blockers	Metoprolol	CHLORTALIDONE;METOPROLOL;TELMISARTAN
Beta-blockers	Metoprolol	CILNIDIPINE;METOPROLOL
Beta-blockers	Metoprolol	CILNIDIPINE;METOPROLOL SUCCINATE
Beta-blockers	Metoprolol	CILNIDIPINE;METOPROLOL SUCCINATE;TELMISARTAN
Beta-blockers	Metoprolol	CILNIDIPINE;METOPROLOL TARTRATE
Beta-blockers	Metoprolol	CILNIDIPINE;METOPROLOL TARTRATE;TELMISARTAN
Beta-blockers	Metoprolol	CILNIDIPINE;METOPROLOL;TELMISARTAN

Protocol Pharmacologic Category	Drug Class	Preferred Name
Beta-blockers	Metoprolol	FELODIPINE;METOPROLOL
Beta-blockers	Metoprolol	FELODIPINE;METOPROLOL SUCCINATE
Beta-blockers	Metoprolol	HYDRALAZINE HYDROCHLORIDE;HYDROCHLOROTHIAZIDE; METOPROLOL TARTRATE
Beta-blockers	Metoprolol	HYDRALAZINE;HYDROCHLOROTHIAZIDE; METOPROLOL
Beta-blockers	Metoprolol	HYDROCHLOROTHIAZIDE;METOPROLOL
Beta-blockers	Metoprolol	HYDROCHLOROTHIAZIDE;METOPROLOL SUCCINATE
Beta-blockers	Metoprolol	HYDROCHLOROTHIAZIDE;METOPROLOL TARTRATE
Beta-blockers	Metoprolol	ISOSORBIDE MONONITRATE;METOPROLOL
Beta-blockers	Metoprolol	ISOSORBIDE MONONITRATE;METOPROLOL SUCCINATE
Beta-blockers	Metoprolol	IVABRADINE HYDROCHLORIDE;METOPROLOL TARTRATE
Beta-blockers	Metoprolol	IVABRADINE;METOPROLOL
Beta-blockers	Metoprolol	LEVAMLODIPINE BESILATE;METOPROLOL SUCCINATE
Beta-blockers	Metoprolol	LEVAMLODIPINE;METOPROLOL
Beta-blockers	Metoprolol	METOPROLOL
Beta-blockers	Metoprolol	METOPROLOL FUMARATE
Beta-blockers	Metoprolol	METOPROLOL SUCCINATE
Beta-blockers	Metoprolol	METOPROLOL SUCCINATE;METOPROLOL TARTRATE
Beta-blockers	Metoprolol	METOPROLOL SUCCINATE;OLMESARTAN MEDOXOMIL
Beta-blockers	Metoprolol	METOPROLOL SUCCINATE;RAMIPRIL
Beta-blockers	Metoprolol	METOPROLOL SUCCINATE;TELMISARTAN
Beta-blockers	Metoprolol	METOPROLOL TARTRATE
Beta-blockers	Metoprolol	METOPROLOL TARTRATE;NIFEDIPINE
Beta-blockers	Metoprolol	METOPROLOL TARTRATE;OLMESARTAN MEDOXOMIL
Beta-blockers	Metoprolol	METOPROLOL TARTRATE;RAMIPRIL

Protocol Pharmacologic Category	Drug Class	Preferred Name
Beta-blockers	Metoprolol	METOPROLOL TARTRATE;TELMISARTAN
Beta-blockers	Metoprolol	METOPROLOL TARTRATE;TRIMETAZIDINE HYDROCHLORIDE
Beta-blockers	Metoprolol	METOPROLOL;MORPHINE
Beta-blockers	Metoprolol	METOPROLOL;NIFEDIPINE
Beta-blockers	Metoprolol	METOPROLOL;OLMESARTAN
Beta-blockers	Metoprolol	METOPROLOL;OLMESARTAN MEDOXOMIL
Beta-blockers	Metoprolol	METOPROLOL;RAMIPRIL
Beta-blockers	Metoprolol	METOPROLOL;TELMISARTAN
Beta-blockers	Metoprolol	METOPROLOL;TRIMETAZIDINE
Beta-blockers	Bisoprolol	ACETYLSALICYLIC ACID;BISOPROLOL FUMARATE;CANDESARTAN CILEXETIL;HYDROCHLOROTHIAZIDE;ROSUVASTATIN CALCIUM
Beta-blockers	Bisoprolol	ACETYLSALICYLIC ACID;BISOPROLOL;CANDESARTAN;HYDROCHLOROTHIAZIDE;ROSUVASTATIN
Beta-blockers	Atenolol	ACETYLSALICYLIC ACID;ATENOLOL;HYDROCHLOROTHIAZIDE;RAMIPRIL;SIMVASTATIN
Beta-blockers	Atenolol	ALPRAZOLAM;ATENOLOL
Beta-blockers	Atenolol	AMILORIDE HYDROCHLORIDE;ATENOLOL;HYDROCHLOROTHIAZIDE
Beta-blockers	Atenolol	AMILORIDE;ATENOLOL;CHLORTALIDONE
Beta-blockers	Atenolol	AMILORIDE;ATENOLOL;HYDROCHLOROTHIAZIDE
Beta-blockers	Atenolol	AMLODIPINE BESILATE;ATENOLOL
Beta-blockers	Atenolol	AMLODIPINE BESILATE;ATENOLOL;CHLORTALIDONE
Beta-blockers	Atenolol	AMLODIPINE;ATENOLOL
Beta-blockers	Atenolol	AMLODIPINE;ATENOLOL;CHLORTALIDONE
Beta-blockers	Atenolol	ATENOLOL
Beta-blockers	Atenolol	ATENOLOL HYDROCHLORIDE

Protocol Pharmacologic Category	Drug Class	Preferred Name
Beta-blockers	Atenolol	ATENOLOL HYDROCHLORIDE;BENDROFLUMETHIAZIDE; HYDRALAZINE
Beta-blockers	Atenolol	ATENOLOL HYDROCHLORIDE;CHLORTALIDONE
Beta-blockers	Atenolol	ATENOLOL;BENDROFLUMETHIAZIDE
Beta-blockers	Atenolol	ATENOLOL;BENDROFLUMETHIAZIDE; HYDRALAZINE
Beta-blockers	Atenolol	ATENOLOL;CHLORTALIDONE
Beta-blockers	Atenolol	ATENOLOL;CHLORTALIDONE;HYDRALAZINE
Beta-blockers	Atenolol	ATENOLOL;CHLORTALIDONE;HYDRALAZINE HYDROCHLORIDE
Beta-blockers	Atenolol	ATENOLOL;CHLORTALIDONE;NIFEDIPINE
Beta-blockers	Atenolol	ATENOLOL;CHLORTALIDONE;NITRENDIPINE
Beta-blockers	Atenolol	ATENOLOL;HYDROCHLOROTHIAZIDE
Beta-blockers	Atenolol	ATENOLOL;HYDROCHLOROTHIAZIDE;LOSARTAN
Beta-blockers	Atenolol	ATENOLOL;HYDROCHLOROTHIAZIDE;LOSARTAN POTASSIUM
Beta-blockers	Atenolol	ATENOLOL;INDAPAMIDE
Beta-blockers	Atenolol	ATENOLOL;ISOSORBIDE MONONITRATE
Beta-blockers	Atenolol	ATENOLOL;LERCANIDIPINE
Beta-blockers	Atenolol	ATENOLOL;LERCANIDIPINE HYDROCHLORIDE
Beta-blockers	Atenolol	ATENOLOL;LEVAMLODIPINE
Beta-blockers	Atenolol	ATENOLOL;LEVAMLODIPINE BESILATE
Beta-blockers	Atenolol	ATENOLOL;LOSARTAN
Beta-blockers	Atenolol	ATENOLOL;LOSARTAN POTASSIUM
Beta-blockers	Atenolol	ATENOLOL;NIFEDIPINE
Beta-blockers	Atenolol	ATENOLOL;NITRENDIPINE
Beta-blockers	Nadolol	BENDROFLUMETHIAZIDE;NADOLOL
Beta-blockers	Nadolol	NADOLOL
Beta-blockers	Propranolol	ALPRAZOLAM;PROPRANOLOL
Beta-blockers	Propranolol	ALPRAZOLAM;PROPRANOLOL HYDROCHLORIDE

Protocol Pharmacologic Category	Drug Class	Preferred Name
Beta-blockers	Propranolol	AMOBARBITAL SODIUM;ATROPA BELLA-DONNA EXTRACT;CLAVICEPS PURPUREA EXTRACT;PROPRANOLOL
Beta-blockers	Propranolol	AMOBARBITAL;ATROPA BELLA-DONNA;CLAVICEPS PURPUREA;PROPRANOLOL
Beta-blockers	Propranolol	ATROPINE SULFATE;CRATAEGUS SPP. LEAF WITH FLOWER;PROPRANOLOL HYDROCHLORIDE;VALERIANA OFFICINALIS ROOT
Beta-blockers	Propranolol	ATROPINE;CRATAEGUS SPP.;PROPRANOLOL;VALERIANA OFFICINALIS
Beta-blockers	Propranolol	BENDROFLUMETHIAZIDE;HYDRALAZINE HYDROCHLORIDE;PROPRANOLOL HYDROCHLORIDE
Beta-blockers	Propranolol	BENDROFLUMETHIAZIDE;HYDRALAZINE; PROPRANOLOL
Beta-blockers	Propranolol	BENDROFLUMETHIAZIDE;PROPRANOLOL
Beta-blockers	Propranolol	BENDROFLUMETHIAZIDE;PROPRANOLOL HYDROCHLORIDE
Beta-blockers	Propranolol	BENZALKONIUM CHLORIDE;PROPRANOLOL HYDROCHLORIDE
Beta-blockers	Propranolol	BENZALKONIUM;PROPRANOLOL
Beta-blockers	Propranolol	CAFFEINE;PHENYTOIN SODIUM;PROPRANOLOL HYDROCHLORIDE
Beta-blockers	Propranolol	CAFFEINE;PHENYTOIN;PROPRANOLOL
Beta-blockers	Propranolol	CAFFEINE;PROPRANOLOL
Beta-blockers	Propranolol	CHLORTALIDONE;NIFEDIPINE;PROPRANOLOL
Beta-blockers	Propranolol	CHLORTALIDONE;NIFEDIPINE;PROPRANOLOL HYDROCHLORIDE
Beta-blockers	Propranolol	CLONAZEPAM;PROPRANOLOL
Beta-blockers	Propranolol	CLONAZEPAM;PROPRANOLOL HYDROCHLORIDE
Beta-blockers	Propranolol	DIAZEPAM;PROPRANOLOL
Beta-blockers	Propranolol	DIAZEPAM;PROPRANOLOL HYDROCHLORIDE
Beta-blockers	Propranolol	DIHYDRALAZINE SULFATE;PROPRANOLOL HYDROCHLORIDE
Beta-blockers	Propranolol	DIHYDRALAZINE;PROPRANOLOL

Protocol Pharmacologic Category	Drug Class	Preferred Name
Beta-blockers	Propranolol	ETIZOLAM;PROPRANOLOL
Beta-blockers	Propranolol	ETIZOLAM;PROPRANOLOL HYDROCHLORIDE
Beta-blockers	Propranolol	HYDRALAZINE HYDROCHLORIDE;PROPRANOLOL HYDROCHLORIDE
Beta-blockers	Propranolol	HYDRALAZINE;PROPRANOLOL
Beta-blockers	Propranolol	HYDROCHLOROTHIAZIDE;PROPRANOLOL
Beta-blockers	Propranolol	HYDROCHLOROTHIAZIDE;PROPRANOLOL HYDROCHLORIDE
Beta-blockers	Propranolol	HYDROCHLOROTHIAZIDE;PROPRANOLOL HYDROCHLORIDE;TRIAMTERENE
Beta-blockers	Propranolol	HYDROCHLOROTHIAZIDE;PROPRANOLOL; TRIAMTERENE
Beta-blockers	Propranolol	NIFEDIPINE;PROPRANOLOL
Beta-blockers	Propranolol	NIFEDIPINE;PROPRANOLOL HYDROCHLORIDE
Beta-blockers	Propranolol	PENTAERITHRITYL TETRANITRATE;PROPRANOLOL
Beta-blockers	Propranolol	PENTAERITHRITYL TETRANITRATE;PROPRANOLOL HYDROCHLORIDE
Beta-blockers	Propranolol	PROPRANOLOL
Beta-blockers	Propranolol	PROPRANOLOL HYDROCHLORIDE
Beta-blockers	Propranolol	PROPRANOLOL HYDROCHLORIDE;SPIRONOLACTONE
Beta-blockers	Propranolol	PROPRANOLOL;SPIRONOLACTONE
Beta-blockers	Timolol	ACECLIDINE HYDROCHLORIDE;TIMOLOL MALEATE
Beta-blockers	Timolol	ACECLIDINE;TIMOLOL
Beta-blockers	Timolol	AMILORIDE HYDROCHLORIDE;HYDROCHLOROTHIAZIDE; TIMOLOL MALEATE
Beta-blockers	Timolol	AMILORIDE;HYDROCHLOROTHIAZIDE;TIMOLOL
Beta-blockers	Timolol	BENDROFLUMETHIAZIDE;TIMOLOL
Beta-blockers	Timolol	BENDROFLUMETHIAZIDE;TIMOLOL MALEATE
Beta-blockers	Timolol	BENZALKONIUM CHLORIDE;SODIUM HYDROXIDE;SODIUM PHOSPHATE DIBASIC;SODIUM PHOSPHATE MONOBASIC (ANHYDROUS);TIMOLOL MALEATE

Protocol Pharmacologic Category	Drug Class	Preferred Name
Beta-blockers	Timolol	BENZALKONIUM CHLORIDE;TIMOLOL MALEATE
Beta-blockers	Timolol	BENZALKONIUM;SODIUM HYDROXIDE;SODIUM PHOSPHATE;SODIUM PHOSPHATE MONOBASIC (ANHYDROUS);TIMOLOL
Beta-blockers	Timolol	BENZALKONIUM;TIMOLOL
Beta-blockers	Timolol	BIMATOPROST;BRIMONIDINE TARTRATE;TIMOLOL MALEATE
Beta-blockers	Timolol	BIMATOPROST;BRIMONIDINE;TIMOLOL
Beta-blockers	Timolol	BIMATOPROST;TIMOLOL
Beta-blockers	Timolol	BIMATOPROST;TIMOLOL MALEATE
Beta-blockers	Timolol	BRIMONIDINE TARTRATE;DORZOLAMIDE HYDROCHLORIDE;TIMOLOL MALEATE
Beta-blockers	Timolol	BRIMONIDINE TARTRATE;DORZOLAMIDE;LATANOPROST; TIMOLOL MALEATE
Beta-blockers	Timolol	BRIMONIDINE TARTRATE;DORZOLAMIDE;TIMOLOL MALEATE
Beta-blockers	Timolol	BRIMONIDINE TARTRATE;TIMOLOL
Beta-blockers	Timolol	BRIMONIDINE TARTRATE;TIMOLOL MALEATE
Beta-blockers	Timolol	BRIMONIDINE;DORZOLAMIDE;LATANOPROST; TIMOLOL
Beta-blockers	Timolol	BRIMONIDINE;DORZOLAMIDE;TIMOLOL
Beta-blockers	Timolol	BRIMONIDINE;TIMOLOL
Beta-blockers	Timolol	BRINZOLAMIDE;TIMOLOL
Beta-blockers	Timolol	BRINZOLAMIDE;TIMOLOL MALEATE
Beta-blockers	Timolol	DORZOLAMIDE HYDROCHLORIDE;TIMOLOL
Beta-blockers	Timolol	DORZOLAMIDE HYDROCHLORIDE;TIMOLOL MALEATE
Beta-blockers	Timolol	DORZOLAMIDE;TIMOLOL
Beta-blockers	Timolol	DORZOLAMIDE;TIMOLOL MALEATE
Beta-blockers	Timolol	EUCALYPTUS GLOBULUS OIL;MENTHA X PIPERITA OIL;PINUS MUGO OIL;TIMOLOL MALEATE;TOCOPHERYL ACETATE

Protocol Pharmacologic Category	Drug Class	Preferred Name
Beta-blockers	Timolol	EUCALYPTUS GLOBULUS;MENTHA X PIPERITA;PINUS MUGO;TIMOLOL;TOCOPHEROL
Beta-blockers	Timolol	HYALURONATE SODIUM;TIMOLOL MALEATE
Beta-blockers	Timolol	HYALURONIC ACID;TIMOLOL
Beta-blockers	Timolol	HYDROCHLOROTHIAZIDE;TIMOLOL
Beta-blockers	Timolol	HYDROCHLOROTHIAZIDE;TIMOLOL MALEATE
Beta-blockers	Timolol	HYPROMELLOSE;TIMOLOL
Beta-blockers	Timolol	HYPROMELLOSE;TIMOLOL MALEATE
Beta-blockers	Timolol	LATANOPROST;TIMOLOL
Beta-blockers	Timolol	LATANOPROST;TIMOLOL MALEATE
Beta-blockers	Timolol	PILOCARPINE HYDROCHLORIDE;TIMOLOL MALEATE
Beta-blockers	Timolol	PILOCARPINE NITRATE;TIMOLOL MALEATE
Beta-blockers	Timolol	PILOCARPINE;TIMOLOL
Beta-blockers	Timolol	PILOCARPINE;TIMOLOL MALEATE
Beta-blockers	Timolol	TAFLUPROST;TIMOLOL
Beta-blockers	Timolol	TAFLUPROST;TIMOLOL MALEATE
Beta-blockers	Timolol	TIMOLOL
Beta-blockers	Timolol	TIMOLOL HEMIHYDRATE
Beta-blockers	Timolol	TIMOLOL MALEATE
Beta-blockers	Timolol	TIMOLOL MALEATE, R-ENANTIOMER
Beta-blockers	Timolol	TIMOLOL MALEATE, S-ENANTIOMER
Beta-blockers	Timolol	TIMOLOL MALEATE;TRAVOPROST
Beta-blockers	Timolol	TIMOLOL;TRAVOPROST
Calcium channel blocker	Flunarizine	DIHYDROERGOCRISTINE MESILATE;FLUNARIZINE DIHYDROCHLORIDE
Calcium channel blocker	Flunarizine	DIHYDROERGOCRISTINE;FLUNARIZINE
Calcium channel blocker	Flunarizine	DOMPERIDONE;FLUNARIZINE DIHYDROCHLORIDE;PARACETAMOL
Calcium channel blocker	Flunarizine	DOMPERIDONE;FLUNARIZINE;PARACETAMOL

Protocol Pharmacologic Category	Drug Class	Preferred Name
Calcium channel blocker	Flunarizine	FLUNARIZINE
Calcium channel blocker	Flunarizine	FLUNARIZINE BETADDEX
Calcium channel blocker	Flunarizine	FLUNARIZINE DIHYDROCHLORIDE
Calcium channel blocker	Flunarizine	FLUNARIZINE DIHYDROCHLORIDE;NICERGOLINE
Calcium channel blocker	Flunarizine	FLUNARIZINE DIHYDROCHLORIDE;PROPRANOLOL HYDROCHLORIDE
Calcium channel blocker	Flunarizine	FLUNARIZINE;NICERGOLINE
Calcium channel blocker	Flunarizine	FLUNARIZINE;PROPRANOLOL
Calcium channel blocker	Lomerizine	LOMERIZINE
Calcium channel blocker	Lomerizine	LOMERIZINE HYDROCHLORIDE
Calcium channel blocker	Verapamil	CAPTOPRIL;VERAPAMIL
Calcium channel blocker	Verapamil	CAPTOPRIL;VERAPAMIL HYDROCHLORIDE
Calcium channel blocker	Verapamil	DIAZEPAM;VERAPAMIL
Calcium channel blocker	Verapamil	DIAZEPAM;VERAPAMIL HYDROCHLORIDE
Calcium channel blocker	Verapamil	DIGOXIN;TRIMETOZINE;VERAPAMIL
Calcium channel blocker	Verapamil	DIGOXIN;TRIMETOZINE;VERAPAMIL HYDROCHLORIDE
Calcium channel blocker	Verapamil	HYDROCHLOROTHIAZIDE;TRIAMTERENE; VERAPAMIL
Calcium channel blocker	Verapamil	HYDROCHLOROTHIAZIDE;TRIAMTERENE; VERAPAMIL HYDROCHLORIDE
Calcium channel blocker	Verapamil	HYDROCHLOROTHIAZIDE;VERAPAMIL

Protocol Pharmacologic Category	Drug Class	Preferred Name
Calcium channel blocker	Verapamil	HYDROCHLOROTHIAZIDE;VERAPAMIL HYDROCHLORIDE
Calcium channel blocker	Verapamil	ISOSORBIDE DINITRATE;VERAPAMIL
Calcium channel blocker	Verapamil	ISOSORBIDE DINITRATE;VERAPAMIL HYDROCHLORIDE
Calcium channel blocker	Verapamil	PENTOBARBITAL;VERAPAMIL
Calcium channel blocker	Verapamil	PENTOBARBITAL;VERAPAMIL HYDROCHLORIDE
Calcium channel blocker	Verapamil	PROSCILLARIDIN;VERAPAMIL
Calcium channel blocker	Verapamil	PROSCILLARIDIN;VERAPAMIL HYDROCHLORIDE
Calcium channel blocker	Verapamil	QUINIDINE BISULFATE;VERAPAMIL HYDROCHLORIDE
Calcium channel blocker	Verapamil	QUINIDINE;VERAPAMIL
Calcium channel blocker	Verapamil	TRANDOLAPRIL;VERAPAMIL
Calcium channel blocker	Verapamil	TRANDOLAPRIL;VERAPAMIL HYDROCHLORIDE
Calcium channel blocker	Verapamil	VERAPAMIL
Calcium channel blocker	Verapamil	VERAPAMIL HYDROCHLORIDE
Angiotensin receptor blocker (ARB)	Candesartan	AMLODIPINE BESILATE;CANDESARTAN CILEXETIL
Angiotensin receptor blocker (ARB)	Candesartan	AMLODIPINE BESILATE;CANDESARTAN CILEXETIL;HYDROCHLOROTHIAZIDE
Angiotensin receptor blocker (ARB)	Candesartan	AMLODIPINE;ATORVASTATIN;CANDESARTAN

Protocol Pharmacologic Category	Drug Class	Preferred Name
Angiotensin receptor blocker (ARB)	Candesartan	AMLODIPINE;CANDESARTAN
Angiotensin receptor blocker (ARB)	Candesartan	AMLODIPINE;CANDESARTAN CILEXETIL
Angiotensin receptor blocker (ARB)	Candesartan	AMLODIPINE;CANDESARTAN CILEXETIL;HYDROCHLOROTHIAZIDE
Angiotensin receptor blocker (ARB)	Candesartan	AMLODIPINE;CANDESARTAN; HYDROCHLOROTHIAZIDE
Angiotensin receptor blocker (ARB)	Candesartan	CANDESARTAN
Angiotensin receptor blocker (ARB)	Candesartan	CANDESARTAN CILEXETIL
Angiotensin receptor blocker (ARB)	Candesartan	CANDESARTAN CILEXETIL;FELODIPINE
Angiotensin receptor blocker (ARB)	Candesartan	CANDESARTAN CILEXETIL;HYDROCHLOROTHIAZIDE
Angiotensin receptor blocker (ARB)	Candesartan	CANDESARTAN CILEXETIL;HYDROCHLOROTHIAZIDE; ROSUVASTATIN CALCIUM
Angiotensin receptor blocker (ARB)	Candesartan	CANDESARTAN CILEXETIL;ROSUVA STATIN CALCIUM
Angiotensin receptor blocker (ARB)	Candesartan	CANDESARTAN;FELODIPINE
Angiotensin receptor blocker (ARB)	Candesartan	CANDESARTAN;HYDROCHLOROTHIAZIDE

Protocol Pharmacologic Category	Drug Class	Preferred Name
Angiotensin receptor blocker (ARB)	Candesartan	CANDESARTAN;HYDROCHLOROTHIAZIDE; ROSUVASTATIN
Angiotensin receptor blocker (ARB)	Candesartan	CANDESARTAN;ROSUVASTATIN
Angiotensin converting enzyme (ACE) inhibitor	Lisinopril	LISINOPRIL
Angiotensin converting enzyme (ACE) inhibitor	Lisinopril	LISINOPRIL DIHYDRATE
Serotonin-norepinephrine reuptake inhibitor (SNRI)	Desvenlafaxine	DESVENLAFAXINE
Serotonin-norepinephrine reuptake inhibitor (SNRI)	Desvenlafaxine	DESVENLAFAXINE BENZOATE
Serotonin-norepinephrine reuptake inhibitor (SNRI)	Desvenlafaxine	DESVENLAFAXINE FUMARATE
Serotonin-norepinephrine reuptake inhibitor (SNRI)	Desvenlafaxine	DESVENLAFAXINE SUCCINATE
Serotonin-norepinephrine reuptake inhibitor (SNRI)	Desvenlafaxine	DESVENLAFAXINE SUCCINATE MONOHYDRATE
Serotonin-norepinephrine reuptake inhibitor (SNRI)	Venlafaxine	VENLAFAXINE

Protocol Pharmacologic Category	Drug Class	Preferred Name
Serotonin- norepinephrine reuptake inhibitor (SNRI)	Venlafaxine	VENLAFAXINE BESYLATE MONOHYDRATE
Serotonin- norepinephrine reuptake inhibitor (SNRI)	Venlafaxine	VENLAFAXINE HYDROCHLORIDE
Miscellaneous	Pizotifen	NICOTINAMIDE;PIZOTIFEN MALATE;PYRIDOXINE HYDROCHLORIDE;RIBOFLAVIN SODIUM PHOSPHATE;THIAMINE HYDROCHLORIDE
Miscellaneous	Pizotifen	NICOTINAMIDE;PIZOTIFEN MALATE;PYRIDOXINE HYDROCHLORIDE;RIBOFLAVIN;THIAMINE HYDROCHLORIDE
Miscellaneous	Pizotifen	NICOTINAMIDE;PIZOTIFEN MALATE;PYRIDOXINE;RIBOFLAVIN;THIAMINE
Miscellaneous	Pizotifen	NICOTINAMIDE;PIZOTIFEN;PYRIDOXINE; RIBOFLAVIN;THIAMINE
Miscellaneous	Pizotifen	PIZOTIFEN
Miscellaneous	Pizotifen	PIZOTIFEN HYDROCHLORIDE
Miscellaneous	Pizotifen	PIZOTIFEN MALATE

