List of Migraine preventive Medications with Proven Efficacy

Below is a list of migraine-preventive medications considered effective or probably effective sorted by mechanism of action. Of note, topiramate and valproic acid derivatives are considered separate categories. A history of inadequate response to greater than 4 of these medications (2 of which have different mechanisms of action) will exclude the subject from the study.

Pharmacologic Category	Drug Name
Antiepileptic	Divalproex sodium ^a , valproic acid, sodium valproate Topiramate
Tricyclic antidepressant	Amitriptyline Nortriptyline
Beta-blockers	Metoprolol Bisoprolol Atenolol Nadolol Propranolol Timolol ^a
Calcium channel blocker	Flunarizine ^a Lomerizine Verapamil
Angiotensin receptor blocker (ARB)	Candesartan
Angiotensin converting enzyme (ACE) inhibitor	Lisinopril
Serotonin-norepinephrine reuptake inhibitor (SNRI)	Desvenlafaxine ^a Venlafaxine
Miscellaneous	Pizotifen ^a

Source: Evers 2009, Hoffmann 2014, Schürks 2008, Silberstein 2012, Steiner 2007¹⁸⁻²²

a. Not approved in Japan

Criteria for Determining Inadequate Response to a Prior Migraine Preventive Medication

Failure of a migraine-preventive medication can be assessed on the basis of efficacy or tolerability and is based on investigator judgment. The criteria below should be used to determine eligibility related to the number of prior failed migraine-preventive medications with unique mechanisms of action.

For efficacy:

- Failure is defined as no meaningful reduction in frequency of migraine days after an adequate trial of at least 2 months at generally accepted therapeutic doses, per investigator judgment and subject interview.
- Medications should have been taken within the past 7 years.

For tolerability:

- Failure is defined as discontinuation of a drug treatment due to adverse effects.
- In assessing failure of a migraine preventive drug on the basis of inadequate tolerability, the entire medical history can be considered. For example, a subject who tried and discontinued topiramate 10 years ago for cognitive clouding should be considered to have failed this treatment.

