The change from baseline to each postbaseline month in monthly migraine days will be analyzed using a mixed model for repeated measures (MMRM). The statistical model will include treatment group, visit (derived as month), prior exposure (yes/no) to a migraine prevention medication with proven efficacy, and treatment group-by-visit interaction as categorical fixed effects. It will also include the baseline score and baseline-by-visit interaction as covariates. The stratum "prior exposure (yes/no)" will use the actual stratification factor derived from prior medication collected by eCRF. An unstructured covariance matrix will be used to model the covariance of within-subject repeated measurements. If the model does not converge, then the Toeplitz covariance structure will be used. If the model with the Toeplitz covariance structure does not converge, then the compound symmetry covariance structure will be used. The Kenward-Roger approximation⁶ will be used to estimate the denominator degrees of freedom. The analysis will be performed based on all postbaseline values using only the observed cases without imputation of missing values. Only data collected during the double-blind period will be included in the analysis. Subjects are always analyzed based on the treatment group assigned by randomization.

Contrasts will be constructed to obtain the average treatment effects across the 12-week treatment period to compare each atogepant treatment group versus the placebo group. Each treatment effect and treatment comparisons will be estimated by the LS Means and their differences in LS Means, along with their SE and 95% confidence intervals, and the p-value corresponding to the between-treatment group difference.

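### SAP Table E omits single-agent bisoprolol, so a subject whose only proven preventive was bisoprolol is coded as having no prior exposure

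*SAP*

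**What the plan says.** **The protocol list.** Protocol Appendix F gives the beta-blockers with proven efficacy as "Metoprolol Bisoprolol Atenolol Nadolol Propranolol Timolol". Bisoprolol carries no footnote; timolol is the only beta-blocker marked as not approved in Japan. Randomization is stratified by prior exposure as defined through this appendix (Protocol 4.1 and 5.8).

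**The SAP's implementation.** SAP Appendix E introduces Table E with: "According to Appendix F in the protocol, a list of migraine-preventive medications with proven efficacy was identified by the clinical team and coding team". The rule then has two conditions. The first is a name match ("If a subject has taken medications before the screening visit with preferred names in Table E"). The second is that the eCRF classifies the drug as a migraine prevention medication. If both hold the subject is Yes "for this subject, otherwise, it is set as" No.

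**The bisoprolol rows.** There are two: "ACETYLSALICYLIC ACID;BISOPROLOL FUMARATE;CANDESARTAN CILEXETIL;HYDROCHLOROTHIAZIDE;ROSUVASTATIN CALCIUM" and "ACETYLSALICYLIC ACID;BISOPROLOL;CANDESARTAN;HYDROCHLOROTHIAZIDE;ROSUVASTATIN".

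**Where the derived value is used.** SAP 9.3.2 says the prior-exposure term in the primary MMRM "will use the actual stratification factor derived from prior medication collected by eCRF". SAP 5.0 calls the Appendix E result the actual strata, tabulates it beside the IWRS stratum and lists subjects with an incorrect stratum. SAP 9.1 analyses wrongly stratified subjects by actual stratum. SAP 9.6 and Protocol 7.4 use prior exposure as an efficacy subgroup.

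**The concern.** Table E is meant to turn Appendix F into a list of coded names. For bisoprolol it does not. The only bisoprolol names it contains are one five-ingredient product under two spellings. That product also contains candesartan, itself an Appendix F drug, so the bisoprolol rows pick up nobody on the strength of bisoprolol alone.

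If a bisoprolol-only subject was enrolled, three things go wrong together:

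- The covariate in the confirmatory model has the wrong value.
- A correctly randomized subject is reported as a stratification error.
- An exposed subject is counted in the unexposed subgroup. Prior exposure is the only efficacy subgroup factor that the protocol itself names.

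A repair after unblinding would be a post hoc change to a term in the primary model of a study intended to support registration in Japan.

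**Working it through.** **1. Appendix F against Table E.**

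| Appendix F drug | Single-agent name in Table E? |
|---|---|
| Valproic acid, sodium valproate, divalproex | Yes (VALPROIC ACID, VALPROATE SODIUM, VALPROATE SEMISODIUM) |
| Topiramate | Yes |
| Amitriptyline, nortriptyline | Yes |
| Metoprolol, atenolol, nadolol, propranolol, timolol | Yes |
| **Bisoprolol** | **No: 2 rows, both five-drug products** |
| Flunarizine, lomerizine, verapamil | Yes |
| Candesartan, lisinopril | Yes |
| Desvenlafaxine, venlafaxine, pizotifen | Yes |

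Bisoprolol is the only gap.

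**2. Is it a reading artefact?** The two rows follow the last metoprolol row and are followed at once by the first atenolol row. The repeated column header comes only later, after ATENOLOL HYDROCHLORIDE, so no page boundary falls at the gap. The metoprolol and atenolol blocks run alphabetically from products beginning with acetylsalicylic acid through to the single agent. The bisoprolol block stops after its acetylsalicylic acid entries. That is consistent with a truncated dictionary search, although the documents do not give the cause.

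**3. Applying the rule.** Take a subject whose sole Appendix F drug was BISOPROLOL FUMARATE, flagged in the eCRF as migraine prevention. The name is not in Table E, so the subject is No. Under protocol Appendix F the correct value is Yes.

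**4. Possible size.** The documents give no count, so the bisoprolol-only share f is an assumption, and f = 0 is possible.

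- Exposed: 0.70 × 520 = 364. Unexposed: 520 − 364 = 156.
- Miscoded: m = 364f. Share of the coded No stratum: m / (156 + m).

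| f (assumed) | m | Share of coded No stratum |
|---|---|---|
| 0 | 0 | 0% |
| 1% | 3.6 | 3.6/159.6 = 2.3% |
| 3% | 10.9 | 10.9/166.9 = 6.5% |
| 5% | 18.2 | 18.2/174.2 = 10.4% |
| 10% | 36.4 | 36.4/192.4 = 18.9% |

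**5. Effect on power.** First the plan's own figures. With 123 per arm, SD 3 and a shared placebo arm, a Hochberg simulation of 400,000 replicates gives 0.988, 0.939 and 0.880 for 60, 30 and 10 mg, and 0.993 for at least one arm. The SAP states 0.986, 0.937, 0.877 and 0.992, so the table is reproduced closely.

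Next, the miscoding. Let b be the assumed difference in outcome between strata. The coded No share is c = 0.3 + 0.7f, of which a fraction q = 0.3/c is truly unexposed. The added residual variance is c·q(1 − q)·b². In the worst case tried, f = 10% and b = 1.5 days:

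- c = 0.37, q = 0.811, added variance = 0.37 × 0.811 × 0.189 × 2.25 ≈ 0.128.
- SD = √(9 + 0.128) = 3.021.
- Unadjusted power for 10 mg (difference 1.21) moves from 0.886 to 0.881.

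At f = 2% with the same b, it is 0.885 (0.8845, against 0.8855 with no miscoding).

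**6. Effect on the No subgroup.** Take 11 miscoded of 167 (6.6%) and assume that the treatment effect differs by a full day between strata. The subgroup estimate shifts by 0.066 × 1 ≈ 0.07 day. With 167/4 ≈ 42 per arm, its standard error is 3 × √(2/41.75) ≈ 0.66 day. The shift is about one tenth of a standard error.

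**The case against.** The best case on the other side accepts the omission and disputes its reach. Most of that case stands.

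- **Few subjects can be affected.** Three conditions must hold together: bisoprolol was the only Appendix F drug taken, it was not one of the two listed products, and the eCRF classified it as migraine prevention. A subject who also took lomerizine, valproate, propranolol, amitriptyline or topiramate still matches Table E. A subject given bisoprolol for another indication is No with or without the missing rows. A reader might infer that every subject with past bisoprolol use is miscoded; the rule does not do that.
- **The number may be zero.** A reader might infer that the covariate, stratum counts and subgroup are certain to be wrong. They are wrong only if at least one such subject was enrolled, and the documents do not say so.
- **The primary result is not threatened.** Exposure precedes randomization and the rule is the same in every arm.
- **The reach beyond the MMRM is partly inferred.** Only SAP 9.3.2 names the eCRF-derived factor. The ANCOVA, imputation-based, mixed and logistic models say just prior exposure (yes/no). Using the derived value there is the natural reading, supported by SAP 9.1, but it is not stated.
- **The SAP has a check that would expose the gap.** A bisoprolol-only subject with IWRS stratum Yes would appear on the SAP 5.0 listing of incorrect strata. This stands only in part: the listing shows a mismatch but attributes it to randomization, and nothing in the SAP then corrects the derivation.

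None of this answers the central point. Table E is stated to follow Appendix F, and for one drug it does not.

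**Conclusion.** The point holds as a minor specification error: wrong as written, in an operative code list. Any subject whose sole Appendix F preventive was bisoprolol (other than the two listed products), flagged in the eCRF as migraine prevention, is coded No when the protocol makes that subject Yes. The error carries into the primary MMRM covariate, the listing of incorrect strata and the prior-exposure subgroup.

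The number affected is unknown and may be zero. The 1% to 10% shares used above are assumptions with no support in the documents; they only show scale. Even at 10% with a 1.5-day stratum effect, power for 10 mg falls by about half a percentage point. No alpha or sample-size figure changes. A reader might take an error in a primary-model covariate to mean that the treatment comparison is biased. The documents do not support that, because the coding uses only pre-randomization data and takes no account of arm.

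**What to change.** Before database lock and unblinding:

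1. Add BISOPROLOL, BISOPROLOL FUMARATE and any other bisoprolol preferred names in the coding dictionary to Table E and to the programmed code list.
2. Repeat the dictionary search for each Appendix F ingredient and confirm that its single-agent names, base and salt, are in Table E.
3. Run a blinded query of the prior-medication data for subjects whose value changes, and record the count, including zero.
4. State in the SAP that the Appendix E factor is the one used in every model with a prior-exposure term, if that is the intention.

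The cost is a few rows in a SAP appendix, a code-list update and one query. No new data are needed and subjects are not affected. If the lock for the primary analysis has already taken place, report the number affected and show the primary MMRM with the corrected factor as a sensitivity analysis.
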